Abbott

Clinical Investigational Plan
and Statistical Analysis Plan

NCT Number: NCT01593917

Trifecta™ Long Term Follow-Up Study

Long Term Follow-Up Study of the St. Jude Medical Trifecta™ Valve

Study Document No: SJM-CIP-100063, SJM Protocol: 1104

Version A

Date: 09 January 2012

Sponsor: St. Jude Medical, Inc
[name]

Table of Contents

PROTOCOL SUMMARY	4
1.0 Introduction	6
1.1 Valvular Disease Background	6
1.2 Trifecta™ Valve	7
2.0 Study Design Overview.....	7
3.0 Study Objectives and Endpoints	8
3.1 Study Objective	8
3.2 Study Endpoints	8
3.2.1 Primary Endpoint	8
3.2.2 Secondary Endpoint:	8
4.0 Subject Population	8
4.1 Inclusion Criteria.....	8
4.2 Exclusion Criteria.....	8
4.3 Additional study data	8
4.4 Sample Size and Study Duration.....	9
4.5 Method of Enrollment	9
5.0 Confidentiality and Subject Informed Consent	9
and Research Authorization	9
6.0 Study Procedures	9
6.1 Summary of Study Procedures.....	9
7.0 Echocardiography Core Laboratory Procedures.....	10
7.1 Phone Assessment.....	11
7.2 Study Termination	11
7.3 Subject Withdrawal.....	11
7.4 Lost to Follow-Up Procedures	11
8.0 Data Collection and Management.....	11
9.0 Serious Adverse Events (SAE)	12
10.0 Clinical Events Committee (CEC)	13
11.0 Data Analysis.....	13
11.1 Primary Endpoint.....	13
11.2 Secondary Endpoints	14
11.3 Additional Analysis	14
11.4 Analysis of Scientific Soundness	14
12.0 Risk Analysis	15
12.1 Potential Benefits.....	15
12.2 Potential Risks.....	15
13.0 Monitoring Procedures.....	15
13.1 Study Monitors	15
13.2 Monitoring Plan	15
13.3 Compliance	15
14.0 Protocol Modifications.....	16

14.1 Amendments to the Protocol 16
14.2 Deviations from the Protocol 16
15.0 Records & Reports 16
15.1 Study Sponsor 16
15.2 Study Investigators 16
 15.2.1 Record Retention 16
16.0 Regulatory Compliance 17
16.1 Institutional Review Board (IRB)/ Ethics Committee (EC) Approval ... 17
Appendix A: Statistical Analysis Plan 18
Appendix B: Definitions 21
Appendix C: References 25

PROTOCOL SUMMARY

Study Title: Long Term Follow Up Study of the St. Jude Medical Trifecta™ Valve

Study Device: Trifecta™ Valve

Study Purpose: To collect long term follow up study data of the Trifecta™ valve in subjects who had the Trifecta™ valve implanted during the IDE study.

Study Objectives:

Primary Objective:

1. The primary objective is to collect long-term study data including long term valve-related events of the Trifecta™ valve.

Study Endpoints:

Primary Endpoint:

1. Freedom from reoperation due to Structural Valve Deterioration (SVD) at year 10 post implant.

Secondary Endpoint:

1. Freedom from all-cause mortality;
2. Freedom from valve related mortality;
3. Freedom from SVD

Study Design: This is a multi-center, prospective, non-randomized, post marketing study to collect long term follow up study data. It will be conducted in the United States and Canada. Subjects enrolled in this clinical study received the Trifecta™ valve during the investigational study that was conducted to obtain FDA approval.

In parallel to this study, a post-approval study (PAS) mandated by FDA is being conducted at 6 of the IDE sites in which follow-up data through 5 years post-implant is being collected. At the completion of the PAS study these sites and their participating subjects will be invited to participate in this long-term follow-up study.

Subjects meeting the eligibility criteria and who have signed the Subject Informed Consent will undergo an NYHA functional classification assessment, a general clinical assessment and a transthoracic-echocardiogram (TTE)

based on their original Trifecta™ implant date at the following time points: 3 year, 5 year, 7 year and 10 year. The alternate years a phone follow-up will be completed.

Study Population: Subjects previously implanted with a Trifecta™ prosthetic valve at the selected sites during the IDE clinical investigational study and who meet all eligibility criteria will be invited to participate.

Sponsor: St. Jude Medical
[name]

1.0 Introduction

1.1 Valvular Disease Background

Valvular heart disease is responsible for nearly 93,000 valve related operations and 20,000 deaths each year in the United States. It is also the contributing factor for another 42,000 deaths each year. The majority of these cases involve disorders of the aortic valve (63%).ⁱ Specific aortic valvular disorders include: aortic stenosis, aortic regurgitation, or a combination of the two, with aortic stenosis being the leading indication for aortic valve replacement in adults.

The most common cause of aortic stenosis in adults is an idiopathic degenerative calcification process that produces an immobilization of the aortic valve cusps.ⁱⁱ This disease progresses from the base of the cusps to the free edge, eventually causing a reduction in the effective valve area. Other causes include a congenital malformation (often a bicuspid valve) and rheumatic fever. Classic symptoms of aortic stenosis include angina, syncope, dyspnea, heart murmur, fatigue, and heart failure.

Common causes of aortic valve regurgitation include idiopathic aortic dilatation, congenital abnormalities (bicuspid valve), degenerative calcification, rheumatic fever, infective endocarditis, systemic hypertension, dissection of the ascending aorta, Marfan's syndrome, and many others that occur much less frequently.ⁱⁱⁱ Symptoms of aortic regurgitation include angina, syncope, dyspnea, heart murmur, fatigue, and heart failure.

Subjects with either aortic stenosis, regurgitation, or both may remain asymptomatic for many years however, after the onset of symptoms (angina, syncope, or dyspnea); the average survival is less than two to three years.ⁱⁱ Aortic valve replacement (AVR) appears to be the only effective treatment for these subjects.ⁱⁱ For certain subjects with severe aortic regurgitation who are not considered good surgical candidates, therapy with vasodilating agents may provide some benefit.ⁱⁱ

Presently, there are two broad categories of aortic valve prostheses; mechanical and tissue (bioprosthesis). The tilting-disc, and bileaflet are the two basic types of mechanical valve prostheses available today. There is a wide variety of bioprostheses available including: autografts (a valve moved from one anatomical position to another within the same individual), homografts/allografts (human valves or tissue taken from cadavers), and heterografts/xenografts (valves or tissue taken from animals). There are currently several different heterografts available.

Heterografts are primarily constructed from porcine aortic valves that have been preserved and sewn onto a frame (stented) or left intact (stentless). A stented bovine pericardial valve is another type of commonly accepted heterograft.^{iii,iv}

Each valve type, mechanical or tissue, has associated risks and benefits. Mechanical valves are associated with potential lifetime durability but require long-term anticoagulation therapy. Tissue valves are reported to have reduced device durability, but typically do not require long-term anticoagulation therapy and are therefore associated with lower incidence of thromboembolic and hemorrhagic events.^{v,vi} Implanting physicians must not only consider the various valve characteristics when deciding which aortic prosthesis to implant, but also various subject factors including, but not limited to, age, coexisting medical conditions, anticoagulation therapy tolerance, and cardiac physiology.^{ii,iii,iv} As a result, physicians frequently encounter a subject where the choice of valve type is unclear.

1.2 Trifecta™ Valve

Trifecta™ valve sizes 19mm through 29mm were evaluated in the Trifecta™ IDE clinical study.

The Trifecta™ valve was approved in the following geographies.

- U.S. FDA approval April 20th, 2011
- Health Canada approval October 18th, 2010

2.0 Study Design Overview

This is a multi-center, prospective, non-randomized, post marketing study to collect long term follow up study data. It will be conducted in the United States and Canada. Subjects enrolled in this clinical study received the Trifecta™ valve during the IDE study that was conducted to obtain FDA approval.

All previously available study data for all subjects from participating sites will be included in the data set for this study. This will include data collected during the IDE study as well as from the FDA-mandated post-approval study, when available.

Subjects meeting the eligibility criteria and who have signed the Subject Informed Consent will undergo an NYHA functional classification assessment, a general clinical assessment and a transthoracic-echocardiogram (TTE) based on their Trifecta™ implant date at the

following time points: 3 year, 5 year, 7 year and 10 year. The alternate years a phone follow-up will be completed.

3.0 Study Objectives and Endpoints

3.1 Study Objective

The primary objective is to collect long-term study data including long term valve-related events of the Trifecta™ valve.

3.2 Study Endpoints

3.2.1 Primary Endpoint

Freedom from reoperation due to Structural Valve Deterioration (SVD) at year 10 post implant.

3.2.2 Secondary Endpoint:

1. Freedom from all-cause mortality;
2. Freedom from valve related mortality;
3. Freedom from SVD

4.0 Subject Population

4.1 Inclusion Criteria

1. Patient currently has a Trifecta™ valve that was implanted at one of the U.S. or Canadian investigational sites during the Trifecta™ IDE study.
2. Patient met eligibility criteria prior to enrollment in the Trifecta™ IDE study.
3. Patient agrees to complete all required follow-up visits.
4. Patient provided written informed consent prior to any study related procedure, as approved by the governing Institutional Review Board (IRB) or the Ethics Committee (EC) of the investigational site.

4.2 Exclusion Criteria

1. Patient is currently participating or planning to participate in any other study unless approved by SJM.

4.3 Additional study data

Data from the Trifecta™ IDE and PAS studies for all participating subjects will be included in the data sets for this study. See Analysis Population section of the Statistical Analysis Plan in Appendix B.

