Appendix A: Statistical Analysis Plan

Summary

The long term follow up data of the Trifecta™ valve will be collected for summary and analysis.

In this long term follow up study, subjects who had the Trifecta™ valve implanted as part of the IDE study and enroll (refer to section 4.1) in this study will be followed for a minimum of:

- Ten years post-implant or
- Until time of death, explant, lost to follow-up, withdrawal or study termination.

Additionally, all previously available study data (from Trifecta™ IDE and Trifecta™ post approval study (PAS)) for all subjects (who met eligibility criteria prior to enrollment in the Trifecta™ IDE study) from these participating sites will be included in the analysis datasets for this long term study. This includes prior study data for subjects from these participating study sites who died, were explanted, or were lost to follow-up prior to this long term study as well as prior study data for subjects from these participating study sites who do not consent to participation in this long term study.

The summary data of study primary and secondary endpoints will be provided based on CEC adjudication.

In addition, NYHA functional classification and key specific hemodynamic data will also be provided.

Study endpoints

Primary endpoint

1. Freedom from reoperation due to structural valve deterioration (SVD) at 10 years post implant.

Secondary endpoints

1. Freedom from all cause mortality;
2. Freedom from valve related mortality;
3. Freedom from SVD

Sample size

Approximately 13 sites (among these, 6 sites originally from PAS) who participated in the Trifecta™ valve IDE study with approximately 650 active subjects at the end of the IDE study will be approached for participation in this study.

Analysis Population

Attempts will be made to approach all previous Trifecta™ IDE subjects at the sites participating in the long term follow up study (who were actively being followed and who met eligibility criteria prior to enrollment in the Trifecta™ IDE study) for participation in this study.

In addition to the data collected during this long term follow up study, the study analysis datasets will include all previously available study data (from Trifecta™ IDE and Trifecta™ PAS) for all subjects (who met eligibility criteria prior to enrollment in the Trifecta™ IDE study) from sites participating in the long term follow up study and the PAS.

Data Analysis and Reporting

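### Section 4.3 names a narrower analysis set than Section 2.0 and the SAP, and even the SAP's set credits enrollees with unobserved time before consent

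*Combined protocol and SAP*

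**What the plan says.** Four places bear on which subjects are analysed.

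- Section 4.3: "Data from the Trifecta™ IDE and PAS studies for all participating subjects will be included in the data sets for this study". It then adds: "See Analysis Population section of the Statistical Analysis Plan in Appendix B". Appendix B holds the definitions; the SAP is Appendix A.
- Section 2.0: "All previously available study data for all subjects from participating sites will be included in the data set for this study".
- Appendix A, Summary: prior data are kept for subjects at participating sites who "died, were explanted, or were lost to follow-up prior to this long term study as well as prior study data for subjects" at those sites "who do not consent to participation in this long term study".
- Appendix A, Analysis Population: prior data for all eligible subjects "from sites participating in the long term follow up study and the PAS". The Sample size paragraph describes the sites to be approached as "Approximately 13 sites (among these, 6 sites originally from PAS").

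Three other provisions matter. Under Section 4.1 a subject can enrol only if "Patient currently has a Trifecta™ valve that was implanted at one of the U.S. or Canadian investigational sites", and under Section 4.5 enrolment happens at signed consent. Subjects at the PAS sites are invited only once the PAS, which follows to 5 years, is complete (Protocol Summary). The Valve Event Analysis in Appendix A starts Kaplan-Meier time at implant, ends it at the event or last contact, and mentions no delayed entry.

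**The concern.** A subject who died or lost the valve before invitation cannot be a participating subject, so Section 4.3 and the SAP Summary describe different denominators. With an implant-date origin the difference affects the estimates. In a set restricted to enrollees, nobody can have died or been explanted before consent, yet those years count as time at risk. Freedom from death, from valve-related death and from reoperation that removes the valve would all read too high.

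The second issue does not depend on Section 4.3. The SAP adds only prior data for subjects who do not enrol. A subject who dies between last IDE or PAS contact and invitation is censored at that contact. A subject who survives and enrols is credited with the same interval as observed, event-free time.

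**Working it through.** The plan states no event rate, performance goal or entry time, so there is no design figure to reproduce. The sizes below rest on assumptions.

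**Inputs from the documents:** about 13 sites, 6 of them PAS sites; PAS follow-up to year 5; phone contacts scheduled from year 2; time origin at implant.

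**Assumed inputs:** constant mortality λ of 4%, 5.5% or 7% per year; non-PAS entry at year 2 or 3 and PAS entry at year 5; equal site sizes (7:6); all survivors consent.

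**1. Section 4.3 read literally: mortality.** True survival is S(10) = exp(−10λ). An enrollee-only curve from implant reads S(10)/S(e) = exp(−λ(10 − e)) for entry at e, averaged over the two site groups with weights 7·S(e₁) and 6·S(5).

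Example, λ = 0.055, entry at years 3 and 5: the values are exp(−0.385) = 68.05% and exp(−0.275) = 75.96%. The weights are 7 × 0.8479 = 5.935 and 6 × 0.7596 = 4.557. The mix is (5.935 × 68.05 + 4.557 × 75.96)/10.492 = 71.5%, against a true 57.7%.

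| λ | True 10-year survival | Entry at 2 and 5 | Entry at 3 and 5 |
|---|---|---|---|
| 4% | 67.0% | 76.6% (+9.6) | 78.4% (+11.3) |
| 5.5% | 57.7% | 69.3% (+11.6) | 71.5% (+13.8) |
| 7% | 49.7% | 62.6% (+12.9) | 65.2% (+15.5) |

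**2. Section 4.3 read literally: reoperation for SVD.** Assume true 10-year freedom of 90%, cumulative hazard H(t) = −ln(0.9)·(t/10)^k, and that every such reoperation before entry removes the valve. The reading is exp(−(H(10) − H(e))), mixed 7:6 in the same way.

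- k = 2: 91.3% (entry 2 and 5) or 91.6% (entry 3 and 5).
- k = 3: 90.6% or 90.7%.

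The overstatement is 0.6 to 1.6 points. It is small because a rising hazard puts most events after entry. A constant hazard (k = 1) would give about 93.3% for entry at 2 and 5, or 3.3 points.

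**3. SAP set: the gap before consent.** With a gap of g years in which no event can be recorded, the curve loses the factor exp(−λg) and reads exp(−λ(10 − g)).

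| λ | True | g = 0.5 | g = 1 |
|---|---|---|---|
| 4% | 67.0% | 68.4% (+1.4) | 69.8% (+2.7) |
| 5.5% | 57.7% | 59.3% (+1.6) | 61.0% (+3.3) |
| 7% | 49.7% | 51.4% (+1.8) | 53.3% (+3.6) |

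**4. Which remedy works.** In simulated cohorts with no gap and true 10-year survival of 0.75, 0.65 and 0.55 (entry at years 2 and 5), the full site-level set gave 0.746, 0.655 and 0.544. Enrollees alone gave 0.826, 0.764 and 0.665. Enrollees alone with delayed entry gave 0.795, 0.723 and 0.611, because nobody is under observation before the first entry. Delayed entry is therefore needed in addition to the full set, not in place of it.

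**The case against.** The strongest reply is that the SAP already rejects the biased set. Section 4.3 does not say that only participants' data are used, and it sends the reader to the Analysis Population section. There is one SAP and one section of that name, so the wrong letter is clerical; Section 9.0 makes a similar slip by sending the adverse event definitions to Appendix C. This stands. The large mortality bias arises only if the Section 4.3 sentence is applied on its own.

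Three stronger readings are tempting, and the documents do not support them.

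- *Three incompatible populations.* There is one contradiction and one ambiguous phrase. If the PAS phrase means sites in either study, it matches Section 2.0 whenever all 6 PAS sites join.
- *Analysis restricted to sites in both studies.* That would leave 6 of 13 sites, about 650 × 6/13 = 300 active subjects, with confidence intervals √(13/6) = 1.47 times as wide. But Section 2.0 adds PAS data only where available, which presupposes subjects without them, and the SAP Summary covers all participating sites.
- *Every endpoint is guaranteed event-free before consent.* Appendix B lets SVD be diagnosed clinically with the valve in place and counts repairs as reoperations. Neither bars enrolment, and such earlier events would be counted from IDE or PAS data.

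On the gap, Section 6.1 has subjects continue the IDE assessment schedule, so the interval may be short. That limits the size, which the documents leave unknown. It does not supply a rule for handling the interval.

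**Conclusion.** The concern holds as a drafting conflict with one analytic gap behind it. Section 4.3 should not stand beside Section 2.0 and the SAP Summary as written. The appendix pointer is wrong, and the PAS phrase needs a stated meaning.

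A reader might infer that the planned estimates are built on immortal time. They are not, provided the SAP Summary governs. The 10 to 16 points for survival and 0.6 to 1.6 points for the primary endpoint describe only what literal use of Section 4.3 would do under the assumed rates, hazard shapes and entry times. The primary endpoint figure also assumes that every early SVD reoperation removes the valve; valve-preserving repairs would make it smaller. Freedom from SVD is only partly affected, through SVD that leads to death or explant before entry.

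What remains under the SAP's set is the uncounted interval before consent, about 1.4 to 3.6 points of 10-year survival for an assumed gap of 0.5 to 1 year, and nothing if there is no gap.

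**What to change.** 1. Reword Section 4.3 to match the SAP Summary: all eligible IDE implants at every site that joins the long-term study, whether or not the subject enrols. Change its pointer from Appendix B to Appendix A.
2. In the Analysis Population, state that the PAS phrase means sites in either study, with a PAS site that does not join contributing data up to PAS exit.
3. In the Valve Event Analysis, take each subject out of the risk set at last IDE or PAS contact and let enrollees re-enter at consent (delayed entry), on top of the full site-level set.

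The cost is a few sentences and an entry-time variable in the survival code; no new data are needed. The estimates will be slightly less favourable. Delayed entry assumes that enrollees are representative of those still at risk, and it needs some subjects under observation while others are in their gap. The report should therefore show numbers at risk and the distribution of gap lengths.

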4.4 Sample Size and Study Duration

The long term follow-up study will enroll subjects who were previously implanted with the Trifecta™ valve in the IDE study and meet section 4.1 criteria and will be followed for ten (10) years from their Trifecta™ implant procedure or until a final event, such as valve explant, death, or change in status (e.g. lost to follow-up or withdrawal from study).

4.5 Method of Enrollment

Subjects are considered enrolled at the time the informed consent is signed.

5.0 Confidentiality and Subject Informed Consent and Research Authorization

This study will be performed in accordance with applicable confidentiality, privacy and security, and data protection laws

The Investigator, or an individual designated by the Investigator, must obtain written study-specific informed consent and research authorization (using the most recent IRB/REB approved document) from an eligible subject prior to commencing any study-related procedures.

The process of obtaining informed consent must be consistent with the FDA published regulations, the Declaration of Helsinki and the reviewing IRB/EC. The subject or legal guardian must be given the opportunity to ask questions of, and receive satisfactory answers from, the investigator or study personnel prior to signing the consent document.

Subjects will be asked to provide consent so that data can be gathered. After the subject signs the informed consent document, the original is to be filed in the subject's medical record, a copy filed in the subject's study binder, and a copy given to the subject.

6.0 Study Procedures

6.1 Summary of Study Procedures

Subjects will begin follow up visits according to the anniversary date of their Trifecta™ valve implant. However, prior to this visit, the patient must sign the informed consent.

Follow-up assessments will include the following (Refer to Table 7, Schedule of Assessments):

- Transthoracic-echocardiogram (TTE)
- NYHA functional classification assessment to be completed by a Study Investigator
- General clinical assessment
- Serious Adverse Event (SAE) Assessment

Table 7: Schedule of Assessments

	Screening	Year 2,4,6,8, and 9* (± 60 days)	Year 3,5,7 and 10* (± 60 days)	Early Termination
Informed Consent	X			
Echocardiogram			X	X
Clinical Assessment*			X	X
NYHA			X	X
Phone Assessment*		X		
Serious Adverse Events	X	X	X	X

*Subjects will continue the assessment schedule from the IDE study.

7.0 Echocardiography Core Laboratory Procedures

Echocardiography examinations will be conducted at the 3, 5, 7 and 10 year assessments. Each site is responsible for performing the echocardiogram according to the Echocardiography Manual of Operations. Echocardiography examinations will be forwarded to the Echocardiography Core Laboratory for interpretation.

The responsibility of the Echocardiography Core Laboratory is to complete the echocardiography data collection forms and submit these to the Sponsor.

The Echocardiography Core Laboratory will provide the study required interpretation and documentation of each follow-up echocardiogram submitted. SJM will use only the measurements from the Echocardiography Core Laboratory for analysis. If the Core Laboratory determines the echocardiogram is unreadable, the subject may be asked to return for another echocardiogram.

